# 1.4 Rationale for the Current Study

In the present study, adult patients with selected advanced solid tumors with the potential to respond to BET inhibition including NMC, NSCLC with RAS mutations or ALK rearrangement, TNBC, CRPC, and PDAC, will receive OTX015 orally using a 3+3 dose escalation scheme to determine the RD for phase II studies for two different administration regimens.

OTX015, a pan-BET bromodomain inhibitor, shows activity in several preclinical hematologic and somatic cancer models. Meaningful antitumor activity has also been reported in patients with heavily pretreated hematological malignancies in the ongoing phase I clinical study treated with OTX015. Accumulating studies reveal the critical roles of BET bromodomains in cancer development. The first clue linking BRD4 with cancer was identification of the BRD4-NUT fusion oncogene which was recognized as an important mechanism in NMC. Besides the chromosomal rearrangement-induced NMC, other studies have also indicated that BRDs may contribute to cancer development through different mechanisms. Knockdown of BRD4 exhibited a robust antileukemic activity against AML *in vitro* and *in vivo*. Other recent studies with small molecule inhibitors of the BET proteins revealed the critical role of BRD4 in the development of several hematopoietic and somatic cancers. Accordingly, small molecule inhibitors targeting BET, such as OTX015, have been proven to be a promising drug for cancer therapy.

Mutant KRAS is a strong activator of the MAPK and PI3K pathways, and the inhibition of KRAS-dependent MAPK and PI3K pathways results in the dephosphorylation of MYC which contributes to its degradation. Recent studies in NSCLC preclinical models reported that the BET bromodomain inhibitors, OTX015 and its analog JQ1, exert remarkable antitumor activity in NSCLC harboring KRAS mutation. However, the concurrent mutation in KRAS and LKB1 genes abrogates effects of these BET inhibitors. Furthermore, *in vivo* experiments using genetically engineered mouse lung cancer models confirmed that JQ1 prompts tumor regression in mutant Kras mouse lung cancers, and sensitivity both *in vitro* and *in vivo* was found to be mediated by MYC downregulation. OTX015 is also broadly active in several NSCLC cell lines harboring EML4-ALK gene fusion supporting its further clinical development in patients with either KRAS mutated or ALK positive NSCLC.

Myc expression was found to be disproportionally elevated in TNBC, and in primary tumors, Myc signaling was associated with shortened disease-free survival. A recent report on TNBC indicates that the interaction with BRD4 is critical for the oncogenic function of Twist, a key activator of epithelial-mesenchymal transition. In addition pharmacologic inhibition of the Twist-BRD4 association reduces invasion, cancer stem cell-like properties, and tumorigenicity of TNBC cells highlighting the use of OTX015 in this poor prognosis tumor.

In CRPC, the BET inhibitor JQ1 disrupts AR recruitment to target gene loci and functions downstream of AR, and abrogated BRD4 localization to AR target loci and AR-mediated gene transcription. In addition, *in vivo*, BET bromodomain inhibition was found to be more efficient than direct AR antagonism in CRPC xenograft mouse models. As BET inhibition functions downstream of AR, OTX015 may be effective in the context of AR-mediated resistance, including compensatory mechanisms involving related steroid hormone receptors that are also likely to require BET bromodomain function.

PDAC continues to be the leading cause of cancer-related death in part due to limited efficacy of conventional chemotherapy. PDAC cell proliferation in collagen decreased in the presence of BET inhibitors and with transfection with siRNA against BRD4, which is increased in human PDAC tumors, including in cells that had undergone epithelial-to-mesenchymal transition or were resistant to chemotherapy, making OTX015 a potential drug in this pathology.

Preliminary data, from an ongoing phase I clinical trial in advanced hematologic malignancies, show that OTX015 is well tolerated from 10 mg to 120 mg QD (days 1-14, q3w) in AL patients, with no DLT

observed. The dose of 160 mg QD (days 1-14, q3w) may exceed the MTD with 2 out of 3 patients experiencing non-hematologic DLTs (grade 3 diarrhea and grade 3 asthenia, respectively) and will soon be assessed by the SMC. A 120 mg QD (continuous) has been explored concurrently and one patient may have experienced non-blastic aplasia, needing further assessment in three more patients.

For OHM patients, thrombocytopenia emerged as a DLT at 40 mg BID and 120 mg QD (continuous), with 11/13 patients experiencing grade 3-4 thrombocytopenia, including 9 with grade 4 thrombocytopenia leading to treatment interruption. Both of these dose levels/schedules exceed the MTD. Higher trough concentrations achieved with both dose/ schedule may be at least partly responsible for the higher frequency and severity of thrombocytopenia. Other parameters may influence the occurrence and severity of thrombocytopenia, such as bone marrow reserve, estimated by previous ASCT, baseline platelet counts and/or bone marrow involvement.

Evidence of clinically significant antitumor activity has been observed at non-toxic doses in AL patients (including one sustained CR at 40 mg QD and one CRi at 80 mg QD) and also in lymphoma patients (including 3 sustained PRs at 80 mg and 120 mg QD), as well as at the toxic dose of 120 mg QD (continuously).

Optimization of dose and schedule are ongoing before initiating expansion cohorts. In AL, additional patients are being enrolled at 120 mg QD (continuously) and 120 mg QD (days 1-14, q3w), while shorter administration with 160 mg (e.g. Days 1-7, q3w) may be decided by the SMC. In OHM patients, three schedules are being explored simultaneously with additional patients at 80 mg QD (continuously), 120 mg QD (Days 1-14, q3w) and 120 mg QD (5days a week every week). A discontinuous schedule may be necessary to allow prolonged treatment.

#### 1.4.1 Rationale for the Trial Design

The purpose of this trial is to determine the MTD of OTX015 for further phase II trials in patients with selected solid tumors that might benefit from BET inhibition, in order to optimize the dose and schedule in this patient population with non-compromised bone marrow (i.e., without high-dose chemotherapy and autologous stem cell transplantation or bone marrow involvement), which is expected to be higher than the MTD of patients with hematologic malignancies, as well as to generate safety and pharmacokinetic data in this population. Antitumor effects over single and multiple cycles of two different administration regimens will be explored using a 3+3 dose escalation scheme based on DLT assessment, and a cohort expansion.

# 1.4.2 Justification for the Regimens and Starting Dose

#### Regimen 1: Daily continuous

A starting dose of 80 mg OTX015 administered orally once daily on a continuous basis will be used based on the following considerations:

- 1) The 80 mg dose was given safely in the ongoing phase I trial in patients with advanced hematologic malignancies (Study OTX015 104).
- 2) Patients with solid tumors (without compromised bone marrow) are expected to tolerate higher OTX015 doses better than those with hematologic malignancies; thus their MTD is predicted to be higher.
- 3) A single daily dose of 80 mg was chosen instead of a 40 mg BID schedule in light of preliminary results from the phase I study in hematologic malignancies suggesting a degree of schedule-dependency, with higher rates of grade 3-4 thrombocytopenia with the BID schedule, which was dose-limiting in patients with hematologic malignancies other than leukemia.

# Regimen 2: Days 1-7, every 21 days

A starting dose of 100 mg OTX015 administered orally once daily for 7 consecutive days, repeated every 3 weeks will be explored in an attempt to determine if discontinuous drug administration can reduce:

- 1) The incidence and severity of thrombocytopenia which appears to be the most common toxicity of OTX015 in patients with hematologic malignancies, emerging at ≥ 80 mg daily continuous dose after nearly 2 weeks of treatment exposure (grade 3-4 thrombocytopenia occurred in 50% of patients with 28% having a grade 4), with an incidence/severity appearing to increase with dose suggesting a possible schedule-dependency.
- 2) Given that in the ongoing phase I study in patients with advanced hematologic malignancies, severe thrombocytopenia tends to occur after approximately 2 weeks of continuous treatment, and that furthermore a recovery interval of approximately 10 days is required for severe thrombocytopenia to return to lower grades, a discontinuous regimen may be required to allow re-treatment every 3 weeks. This is important to take into account for future combination clinical studies.

These two regimens (with or without recovery period) will be tested in parallel, i.e., Regimen 1 (daily continuous dosing) and Regimen 2 (7 days every 21 days). This will allow selection of the optimal regimen for further studies in terms of balance between tolerability, pharmacokinetics and antitumor activity.

#### 2 STUDY OBJECTIVES

# 2.1 Primary Objective

To determine the Maximal Tolerated Dose (MTD) defined as the recommended phase II dose for two
distinct regimens of OTX015/MK-8628 administered orally to patients with selected advanced solid
tumors.

# 2.2 Secondary Objectives

- To assess the safety profile of single-agent OTX015/MK-8628
- To characterize pharmacokinetics parameters of OTX015/MK-8628
- To determine the antitumor activity of OTX015/MK-8628 in selected solid tumors

#### 3 STUDY DESIGN, DURATION AND DATES

#### 3.1 Study Design

This is an open-label, multicentric, international, non-randomized phase I trial with dose optimization of single-agent OTX015/MK-8628 administered *per os* in patients with selected advanced tumors (NMC, TNBC, NSCLC, CRPC and PDAC).

The study will be performed in two parts. In the first part a dose escalation study will be performed evaluating two regimens in parallel to establish the MTD in each of the selected indications. In the second part, the efficacy of OTX015/MK-8628 will be evaluated in expansion cohorts of each of the five indications using a selected regimen. Patients will be included in at least seven centers worldwide.

The two regimens evaluated in parallel in the dose escalation part are:

Regimen 1: continuous, once daily for 21 consecutive days (21-day cycles), at a starting dose of 80 mg/day.

Regimen 2: once daily on days 1 to 7, repeated every 3 weeks (21-day cycles; 1 week ON/2 weeks OFF), at a starting dose of 100 mg/day.

A sequential accrual design with standard dose escalation is used. Patients will be included in the next available regimen.

Up to four dose levels will be evaluated for each regimen.

Regimen 1: 80, 100, 120 and 160 mg/day, continuous, 21-day cycles

Regimen 2: 100, 120, 160 and 200 mg/day, 1 week ON/2 weeks OFF, 21-day cycles

Patients will undergo a dose and/or schedule modification in the event of toxicity.

Three patients will be enrolled per dose level, and up to three additional patients at the first occurrence of a DLT (see Section 5.2.4) during the first 21 days of treatment. Up to 48 patients evaluable for DLT will be enrolled in the dose escalation part (24 for each regimen).

The MTD will be the dose level at which fewer than one-third of the patients experience DLT during the first 21 days, and is defined as the DL at which 0 out of 3 patients or 1 out of 6 patients experiences DLT, with the next higher DL having at least 2 out of 3 to 6 patients having DLT.

Once the MTD is established for each regimen and at least 3 patients have received at least two evaluable cycles of study drug at the MTD, an expansion step will be initiated to assess the efficacy of OTX015/MK-

8628 in these populations, as measured by clinical benefit (CR, PR or SD, according to RECIST v1.1 or PCWG2). Up to 50 evaluable patients (10 per indication) will be accrued in the expansion phase.

# 3.2 Independent Safety and Data Monitoring Committee

The SMC will be composed of the principal investigators of each participating center, the pharmacokinetics (PK) specialist, medical and safety representatives of the Sponsor and an independent expert in the field of oncology early drug development (see Appendix 4). All decisions made by the SMC and their rationale will be recorded.

The SMC will be responsible for the following decisions:

- Proceeding to the next higher DL or stopping dose escalation
- Adding patients at a given DL
- Determining the MTD and closing patient enrollment in that dose level and regimen
- Progressing with the dose expansion part
- Selecting the regimen to be followed in each indication in the expansion part of the study
- Performing optional study parts
- Making decisions aimed at improving participating patients' safety.

In addition, according to the nature, suspected relationship to study drug, or other clinical considerations, the SMC will make *ad-hoc* decisions, such as replacing non-evaluable patients, adding more patients at the same DL, adding intermediate DLs, exploring additional doses and/or regimens (e.g., if the MTD is not reached at the highest dose), or not considering a given DLT as clinically relevant for the determination of the MTD. PK results will be forwarded to the SMC as they become available and will be taken into account for the determination of the MTD, notably if no DLT occurs.

#### 3.3 Study Duration and Dates

Patients will begin treatment within a week after registration, followed by the treatment period (3-week cycles), and a follow-up period of at least 2 treatment cycles after the last patient has started treatment.

**Study period:** patients are on the study from the time of Informed Consent Form (ICF) signature until the last visit or death, whichever comes first.

**Treatment period:** the time from the initiation of study therapy until the last study drug intake, plus a 30 day safety observation period during which OTX015/MK-8628-related TEAEs are reported.

**End of study:** the study is considered completed after the last patient has been evaluated for efficacy with a follow-up of at least 2 cycles.

The duration of this study will depend on the number of DLTs encountered in each regimen, the number of dose levels explored in each regimen and the rate of accrual in each of the five expansion cohorts.

The study will be closed after the last visit of the last patient still on study.

#### 4 SELECTION OF PATIENTS

#### 4.1 Number of Patients

The study will be carried out in two steps.

The dose escalation step will explore up to four OTX015/MK-8628 DLs using two regimens to determine the MTD in each regimen. Up to 48 patients evaluable for DLT (i.e. up to 24 patients per regimen) will be accrued depending on the number of DLTs encountered.

Up to 50 additional patients will be included in five expansion cohorts (10 patients per indication).

Overall, the total number of patients expected to be accrued in this study is up to 98 evaluable patients. The final sample size will depend on the number of DLTs encountered at each DL in each regimen, and may be increased if the MTD is not reached for either of the two proposed regimens with the four planned DLs, and additional DLs are required.

#### 4.2 Inclusion Criteria

Patients must fulfill all of the following requirements to enter the study:

- 1. Signed informed consent obtained prior to initiation of any study-specific procedures and treatment;
- 2. Histologically or cytologically confirmed diagnosis of one of the following advanced or metastatic solid tumors for which standard therapy either does not exist or has proven ineffective, intolerable or inacceptable for the patient:
  - NUT midline carcinoma (ectopic expression of NUT protein as determined by IHC and/or detection of BRD-NUT gene translocation as determined by FISH);
  - Triple negative breast cancer defined according to ASCO recommendations (Hammond et al., 2010; Wolff et al., 2007);
  - Non-small cell lung cancer harboring a rearranged ALK gene/fusion protein (FISH or IHC) or KRAS mutation (as defined by any molecular analysis);
  - Castrate-resistant prostate cancer (CRPC);
  - Pancreatic ductal adenocarcinoma;
- 3. At least one measurable lesion as per RECIST version 1.1., except for CRPC patients who may be enrolled with objective evidence of disease as per Prostate Cancer Clinical Trials Working Group (PCWG2) criteria;
- 4. Age  $\geq$  18 years at the time of informed consent;
- 5. Life expectancy  $\geq$  3 months;
- 6. ECOG Performance Status (PS)  $\leq 1$ ;
- 7. Adequate bone marrow reserve, renal and liver function:
  - Absolute neutrophil count  $\geq 1.5 \times 10^9 / L$ ,
  - Platelet count  $\geq 150 \times 10^9 / L$ ,
  - Hemoglobin  $\geq 9$  g/dL (blood transfusion  $\leq 7$  days of screening not permitted),
  - Creatinine clearance ≥ 30 mL/min calculated according to the Cockroft and Gault formula or MDRD formula for patients aged > 65 years,
  - Alanine aminotransferase (ALT), aspartate aminotransferase (AST) < 3 x ULN, if alkaline phosphatase (ALP) > 2.5 X ULN, then liver fraction should be  $\le 2.5$  X ULN, and total bilirubin  $\le 1.25$  x ULN (in case of liver involvement, total bilirubin  $\le 2$  x ULN will be allowed),
  - Serum albumin  $\geq 2.0$  g/dL for NMC,  $\geq 3.0$  g/dL for NSCLC, CRPC, TNBC and pancreatic cancer
  - INR  $\leq 1.5$  or INR  $\leq 3$  for patients treated with antivitamin K;

- 8. An interval of  $\geq 3$  weeks since chemotherapy ( $\geq 6$  weeks for nitrosoureas or mitomycin C), immunotherapy, hormone therapy or any other anticancer therapy or surgical intervention resection, or  $\geq 3$  half-lives for monoclonal antibodies, or  $\geq 5$  half-lives for other non-cytotoxic agents (whichever is longer);
- 9. CRPC patients must maintain ongoing androgen deprivation therapy with a gonadotropin releasing hormone (GnRH) analogue, antagonist or orchiectomy providing serum testosterone is < 50 ng/dL (<1.7 nmol/L);
- 10. Patients receiving bisphosphonate or denosumab therapy must be on stable doses for at least 4 weeks before initiating study treatment.

#### 4.3 Exclusion Criteria

The presence of any of the following criteria excludes a patient from participating in the study:

- 1. Inability to swallow oral medications or presence of a gastrointestinal disorder (e.g. malabsorption) deemed to jeopardize intestinal absorption of OTX015/MK-8628;
- 2. Persistent grade >1 clinically significant toxicities related to prior antineoplastic therapies (except for alopecia); stable sensory neuropathy ≤ grade 2 NCI-CTCAE v. 4.0 is accepted.
- 3. Known primary CNS malignancy or CNS involvement;
- 4. History of prior or concomitant malignancies (other than excised non-melanoma skin cancer or cured *in situ* cervical carcinoma) within 3 years of study entry;
- 5. Other serious illness or medical conditions, such as active infection, unresolved bowel obstruction, or psychiatric disorders;
- 6. Known HIV positivity;
- 7. Participation in another clinical trial or treatment with any investigational drug within 30 days prior to study entry;
- 8. Other concomitant anticancer treatment;
- 9. Concomitant therapy with strong CYP3A4 interfering drugs;
- 10. Current use of anticoagulants (e.g. warfarin, heparin) at therapeutic levels within 7 days prior to the first dose of OTX015/MK-8628. Low-dose (prophylactic) low molecular weight heparin (LMWH) is permitted;
- 11. Pregnant or breast-feeding patients, and men and women with childbearing potential not using effective contraception while on study treatment.

Any waiver of these inclusion and exclusion criteria should be exceptional and justified and must be approved by the investigator and the Sponsor on a case-by-case basis prior to enrolling the patient. This must be documented by both the Sponsor and the investigator.

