Six of the 10 OHM patients with grade 4 thrombocytopenia had previous high dose chemotherapy with autologous stem cell transplantation (ASCT) and/or known bone marrow involvement. Furthermore, platelet counts at baseline, even in the normal range, could predict severe thrombocytopenia. Prior ASCT, bone marrow involvement and baseline platelet count are probably non-independent factors that all reflect bone marrow reserves. Their potential predictive role will be further evaluated and should be clarified.

Days

The mechanism of action of OTX015-induced thrombocytopenia may be complex and will be explored systematically.

Of note, most clinically relevant and treatment-limiting thrombocytopenia in the OHM cohort has been observed at DLs and schedules considered as exceeding the MTD.

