#### 11.3 Analysis Populations

- Evaluable for DLT: patients who receive at least 85% of the planned dose of study drug (18 days for Regimen 1, or 6 days for Regimen 2) or experience DLT during the first 21-day cycle.
- Treated population: patients who receive at least one dose of study drug.
- Evaluable for efficacy: patients who receive at least 2 complete cycles (6 weeks) of treatment and have undergone baseline assessment and one on-study tumor assessment, or who discontinue early due to disease progression.

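### Section 4.3 allows eligibility waivers, including for marrow, renal and liver limits, and a waived patient counts fully in the 3+3 decision with no duty to tell the SMC

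*Protocol*

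**What the plan says.** Protocol 4.2 opens with "Patients must fulfill all of the following requirements to enter the study", and 4.3 with "The presence of any of the following criteria excludes a patient from participating in the study". The closing paragraph of 4.3 then provides: "Any waiver of these inclusion and exclusion criteria should be exceptional and justified and must be approved by the investigator and the Sponsor". Each waiver is to be decided individually, ahead of enrolment, and both parties must record it. The paragraph names no criterion that may not be waived and does not separate dose escalation from expansion. The eligibility lists in the synopsis carry no such paragraph.

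Among the criteria it reaches is "Adequate bone marrow reserve, renal and liver function" (4.2, item 7), which holds the limits for neutrophils, platelets, hemoglobin, creatinine clearance, transaminases and bilirubin.

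The primary endpoint counts patients with a DLT in cycle 1. Protocol 11.3 defines the set as "Evaluable for DLT: patients who receive at least 85% of the planned dose of study drug", or who have a DLT in that cycle. SAP 2.5 uses the same definition and extends it to the BID regimen. Neither makes eligibility a condition. Under Protocol 5.2.3 a patient is replaced only for receiving too little drug, for reasons other than toxicity, without a DLT.

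**The concern.** The thresholds that can be waived include ones that the protocol itself ties to the dose-limiting toxicity. Section 1.4.1 says the MTD is sought "in order to optimize the dose and schedule in this patient population with non-compromised bone marrow". Section 1.3.3.2, reporting the hematology trial, says that "platelet counts at baseline, even in the normal range, could predict severe thrombocytopenia". A borderline patient who misses a marrow, renal or liver limit is a natural candidate for a waiver, and may differ from eligible patients in DLT risk.

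In a cohort of three, that patient is a third of the data. If the outcome enters the count unmarked, the SMC may escalate, expand or stop partly on a patient whom the stated criteria exclude. The recommended dose would then describe a somewhat different population from the one in Section 4. The patient would also carry a risk that the criteria were written to avoid.

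**Working it through.** **1. The plan's own figures.** Escalation maximum: 2 regimens × 4 dose levels × 6 patients = 48, as in Protocol 4.1. Adding 5 indications × 10 = 50 gives 98, also as stated. The SAP total is 48 + 3 × 14 = 90, as stated. No figure in the plan is in dispute, and none describes the effect of a waiver.

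**2. Which criteria the waiver really opens.**

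| Subject | Separate rule outside 4.2 and 4.3? |
|---|---|
| Strong CYP3A4 drugs | Yes: 6.2 and Appendix 3 |
| Curative-level anticoagulation | Yes: 6.2 |
| Other cancer therapy | Yes: 6.2 |
| Pregnancy | Yes: 4.4 |
| Consent | Yes: 12.3 |
| Neutrophils, platelets, hemoglobin, creatinine clearance, transaminases, bilirubin at entry | None found |

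The rules in the first five rows carry no waiver clause, so the exposed part is mainly the last row.

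**3. How a waived patient enters the decision.** Under 5.2.3, 0 of 3 leads to escalation, 1 of 3 to expansion to six, no more than 1 of 6 to escalation, and 2 or more to a halt. One patient adds at most one DLT. Alone, that forces expansion; a halt needs a DLT in another patient too. A waived patient without a DLT helps to make up a 0 of 3.

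**4. Size, by illustration.** The documents give no true DLT rates, so these are assumptions: risk p for eligible patients, risk q for one waived patient among the first three, and the next three all eligible.

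P(escalate) = P(0 of 3) + P(1 of 3) × (1 − p)³

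With p = 0.15 and all eligible:
- P(0 of 3) = 0.85³ = 0.614
- P(1 of 3) = 3 × 0.15 × 0.85² = 0.325
- P(escalate) = 0.614 + 0.325 × 0.614 = 0.814

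With one waived patient at q = 0.40:
- P(0 of 3) = 0.60 × 0.85² = 0.4335
- P(1 of 3) = 0.40 × 0.85² + 0.60 × 2 × 0.15 × 0.85 = 0.289 + 0.153 = 0.442
- P(escalate) = 0.4335 + 0.442 × 0.614 = 0.705

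The difference is about 11 percentage points. The same formula over a range:

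| p | All eligible | One waived, q = 0.40 | One waived, q = 0.50 | One waived, q = 0.05 |
|---|---|---|---|---|
| 0.10 | 0.906 | 0.801 | 0.766 | 0.924 |
| 0.20 | 0.709 | 0.613 | 0.566 | 0.780 |
| 0.30 | 0.494 | 0.448 | 0.401 | 0.611 |

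The last column shows that the effect can run upward. At p = 0.30, close to the one-third limit that Section 3.1 sets for the MTD, one low-risk patient raises the chance of escalating by about 12 points (0.611 − 0.494). Two waived patients at q = 0.40 with p = 0.15 would give 0.590, but two in three hardly fits waivers meant to be exceptional.

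The calculation applies to the 3+3 rule for the two once-daily regimens. The documents give no escalation rule for the BID regimen in the SAP.

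**The case against.** The clause is narrow: exceptional, justified, agreed beforehand and documented by both parties. It reads as a stated exception to a rule, and a synopsis that omits it is a summary and does not contradict it.

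There are also checks. At registration (Protocol 5.4) the CRO's Medical Monitor sees hematology and biochemistry results and can refuse inclusion. The SMC (3.2, Appendix 4) includes the site principal investigators and the Sponsor's medical and safety representatives, so those who approve waivers are largely represented on it. It reviews each cohort's clinical data, validates DLTs, and may add patients or set aside a DLT. A DLT must also be judged drug-related. The risks in the illustration are assumed.

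Most of this stands as mitigation, but it leaves the gap open. Registration is a check, not a bar. The committee can weigh a waiver only if it knows of it, and no text requires that waiver status be presented. Setting aside a DLT corrects in one direction only: it cannot take a DLT-free waived patient out of a 0 of 3.

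Three stronger readings are tempting and are not supported:
- A reader might infer that every criterion is unprotected, including those on interacting drugs and anticoagulants. Step 2 of the working shows that several are barred separately.
- A reader might infer that one waived patient can halt escalation alone. The rule in 5.2.3 requires at least two DLTs.
- A reader might infer that the MTD has in fact been biased. The documents do not say whether any waiver was granted.

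**Conclusion.** The point holds as a gap in design and reporting. The marrow, renal and liver entry limits can be waived, the analysis sets do not recognise a waiver, and the committee that fixes the MTD need not be told. One waived patient can force expansion to six, tip a cohort toward a halt together with another patient's DLT, or contribute to a 0 of 3 escalation.

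Under the assumed risks, one higher-risk patient (q = 0.40 or 0.50) lowers the chance of escalating at a dose level by about 5 to 14 percentage points, and one lower-risk patient (q = 0.05) raises it by about 2 to 12. These figures depend wholly on the assumed p and q and describe a cohort that contains a waived patient. How often that happens cannot be known from the documents. The change is worth making because it is cheap and protects both patients and the primary endpoint.

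**What to change.** 1. Delete the closing paragraph of Protocol 4.3, at least for dose-escalation cohorts, and state that no eligibility waivers are granted there. A criterion that proves too strict is changed by amendment under 12.5.
2. For any patient already entered under a documented waiver, give the SMC the waived criterion before the cohort decision where that decision is still open.
3. In the SAP, add a listing of waived patients (criterion, regimen, dose level, DLT status) and the DLT count per dose level and regimen with and without them. The count without them is descriptive: removing one of three leaves two, to which the 3+3 rule does not apply. If no waiver was granted, one sentence in the report closes the matter.

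The SAP describes part 1 in the past tense and already reports that no response was seen in CRPC, so for completed cohorts item 3 is what remains useful. The duty in 4.3 to document each waiver means the data should exist.

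Cost: a few borderline patients are not enrolled, accrual may slow slightly, and one listing is added. The planned maximum of 48 DLT-evaluable patients does not change.
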